6.1.4 Day 28±3 After Last Study Transfusion or Early Termination

The complete list of assessments to be performed during the Day 28±3 or Early Termination visit are outlined in Table 7.1e.

Subjects should be scheduled for a follow-up visit 28±3 days after the last study transfusion to obtain additional safety information, including subject-reported AEs, SAEs, and laboratory results. This visit may occur either in hospital, clinic visit, or offsite. In certain situations, it is possible for a mobile medical professional, authorized by the Sponsor and requested by site personnel, to conduct a home health service visit at a subject's home to collect these assessments. Blood samples for determination of HLA antibodies will also be collected at the visit and sent for testing at a specialty central laboratory. TRs, AEs and SAEs will be documented for 28 days after the last study transfusion, or earlier if the subject dies prior to Day 28 post last study RBC transfusion. If a subject has been discharged prior to Day 28 post last study RBC transfusion, the vital status, need for RRT and other safety information (e.g., AEs and SAEs) may be obtained through medical records, the subject's physician, or a telephone interview with either the subject or a family member.

Cerus Corporation

Title: A Randomized, Double-Blinded, Controlled, Parallel Group, Non-inferiority, Phase III Study to Evaluate the Efficacy and Safety of the INTERCEPT Blood System for Red Blood Cells in Patients undergoing Complex Cardiac Surgery Procedures (the ReCePI study)

6.1.5 Day 30 – After Surgery Assessment

The complete list of assessments to be performed at Day 30 are outlined in Table 7.1e.

All randomized subjects who receive a study RBC transfusion must have their vital status and need for RRT (defined as hemodialysis or peritoneal dialysis) documented at Day 30 after surgery. RRT that is provided prophylactically during surgery while patient is on a bypass machine (the pump) does not meet this endpoint. The vital status and RRT assessment on Day 30 post surgery can be obtained either from the medical records, from a phone call to the subject or family, or during the visit 28 ± 3 days after the last study transfusion (only if the last study transfusion was given at day 2 or later in the acute transfusion support period).

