Additional endpoints will include mortality or the need for RRT (defined as hemodialysis or peritoneal dialysis) by Day 30 post-surgery; and AKI as defined by modified Kidney Disease Improving Global Outcomes (KDIGO) criteria. Any RRT that is provided prophylactically during surgery while patient is on a bypass machine does not meet this endpoint. The vital status and RRT assessment on Day 30 after surgery can be performed either from the medical records, from a phone call to the subject or family, or during the visit 28 +/- 3 days after the last study transfusion if the window covers 30 days after surgery time point.

Cerus Corporation

Title: A Randomized, Double-Blinded, Controlled, Parallel Group, Non-inferiority, Phase III Study to Evaluate the Efficacy and Safety of the INTERCEPT Blood System for Red Blood Cells in Patients undergoing Complex Cardiac Surgery Procedures (the ReCePI study)

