4.1.2 Secondary Endpoints

- Efficacy: Secondary efficacy endpoints include:
 - The proportion of patients with a diagnosis of stage I, II or III Acute Kidney Injury (KDIGO 2012) based on changes in sCr levels from pre-surgery baseline and the need for renal replacement therapy (RRT) post-surgery.
 - Mortality or the need for RRT by 30 days post completion of surgery.

Safety: Assessment of additional safety parameters in post-surgical subjects transfused with INTERCEPT RBCs compared with subjects transfused with conventional RBCs, include:

- Treatment-emergent AEs through 28 days after the last study transfusion.
- Treatment-emergent SAEs through 28 days after the last study transfusion.
- Transfusion reactions (as defined by the CDC National Healthcare Safety Network [NHSN] Hemovigilance Module protocol) through 28 days after last study transfusion.
- Treatment-emergent immunization to RBC allo-antigens through 28 ± 3 days after the last study transfusion.
- Treatment-emergent immunization to HLA allo-antigens through 28 ± 3 days after the last study transfusion.

[figure not shown]
Cerus Corporation

Title: A Randomized, Double-Blinded, Controlled, Parallel Group, Non-inferiority, Phase III Study to Evaluate the Efficacy and Safety of the INTERCEPT Blood System for Red Blood Cells in Patients undergoing Complex Cardiac Surgery Procedures (the ReCePI study)

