4.4 TREATMENT

Eligible subjects will be consented/provide assent and randomized to receive either INTERCEPT RBCs (Test) or conventional RBCs (Control) which will be transfused as needed starting from surgery at Day 0 until study post-operative Day 7, hospital discharge or death, whichever is first.

Treatment assessments will be divided into an acute transfusion support period starting on the day of surgery (Day 0) until post-operative Day 7, hospital discharge, or death, whichever is first, and a post-surgical follow-up visit (28 ± 3 days) after the last study transfusion to collect additional safety data. A sample for sCr determination will be taken at 48 ± 4 hours after the end of surgery to document the primary efficacy endpoint. For non-transfused subjects, a blood sample for sCr will be drawn at 48 ± 4 hours post-surgery. Patient status with regard to mortality and RRT on Day 30 post surgery will be documented. Anesthesia and surgical procedures will be performed according to the local standards of the institution.

Cerus Corporation

Title: A Randomized, Double-Blinded, Controlled, Parallel Group, Non-inferiority, Phase III Study to Evaluate the Efficacy and Safety of the INTERCEPT Blood System for Red Blood Cells in Patients undergoing Complex Cardiac Surgery Procedures (the ReCePI study)

Study RBC components will be ordered and administered to study subjects by treating physicians, according to the local standards of care. Following the post-surgery 7-day acute transfusion support period, subjects will receive conventional RBC components if additional transfusions are needed, as indicated by their treating physician.

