6.1.6 End of Study (75 ± 15 Days After Last Study Transfusion)

The complete list of assessments to be performed at the 75 ± 15 day study visit are outlined in Table 7.1e.

Subjects should be scheduled for a second follow up visit on Day 75 ± 15 days after the last study transfusion for vital status, need for RRT, and for assessment of INTERCEPT RBC-specific antibodies at end of study, either in hospital, clinic visit or off-site. In certain situations, it is possible for a mobile medical professional, authorized by the Sponsor and requested by site personnel, to conduct a home health service visit at a subject's home to collect these assessments. If the assessment of INTERCEPT RBC-specific antibodies is positive, the positive S-303 specific DSTR should be entered on the Adverse Event eCRF.

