Assessment	28±3 days After last study transfusion or Early Termination	30 days After Surgery	End of Study (75±15 Days After Last Study Transfusion)	Superscripts Defined	
Vital signs (HR, BP, RR)	X			
2. See Table 7.2: Hematology and Chemistry Testing for details on required labs
 
* The adverse event, serious adverse event and transfusion reaction collection period will begin at the start of surgery or the first study RBC transfusion, whichever is first. AEs including protocol specified AEs, TRs and SAEs (see Section 7.3) are collected through 28 days after the last study transfusion; also collected daily during acute transfusion support period. Adverse events (AEs) will not be collected for non-transfused subjects, but vital status will be recorded at the time of discontinuation.
	
Concomitant medications	X				
Hematology panel ²	X				
Blood chemistry ²	X		X		
DAT, IAT	X				
INTERCEPT RBC antibody screen (S-303-specific antibody screen)	X				
Sample for HLA antibodies	X				
All other blood components (including non- study RBCs) transfused, if any	X				
AEs/ SAEs/TRs *	X				
Documentation of vital status and need for RRT	X	X ¹¹	X	
¹¹. Assess at Day 30 post surgery via clinic visit, medical record or phone call. Any RRT that is provided prophylactically during surgery while the subject is on a bypass machine does not meet this endpoint.
	

Table 7.2: Hematology and Chemistry Testing- Required (R) results and Where Available (WA)^a results

Study Period	Screening / Randomization		Acute Transfusion Support Period (Surgery [Day 0] to Post-operative Day 7, hospital discharge or death, whichever is first)		Post-operative Period	Follow-up Visit
		Baseline (Pre-surgery)				
Window	Day -30 to Day -1	Day -1 or Day 0 pre- surgery ^g	Day 0 Surgery	Days 1 – 7, hospital discharge or death	Days 8 to 28 after last study transfusion / death Laboratory results recorded in the eCRFs during this period will only be those assessed as clinically significant per the investigator.	28±3 days after last study transfusion or Premature Discontinuation Visit
Pregnancy test (if applicable)	R ^j	R ^j				
Hematology (CBC):						
Hematocrit (Hct)	R ^b	WA	R	R ^{d,e,i}	WA	R
Hemoglobin (Hb)	R ^b	WA	R	R ^{d,e,i}	WA	R
Platelets (PLT)	R ^b	WA	R	R ^{d,e,i}	WA	R
RBC Count	R ^b	WA	R	R ^{d,e,i}	WA	R
WBC Count	R ^b	WA	R	R ^{d,e,i}	WA	R
Fibrinogen		WA	WA	WA ^d	WA	
Troponin		WA	WA	WA ^d	WA	
Blood chemistry:						
Alkaline Phosphatase (ALP)	WA	WA	WA	WA ^d	WA	WA

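### The rule that lets the 28±3-day visit supply Day 30 mortality/RRT status ignores the −3-day allowance, and Sections 2.5 and 6.1.5 state different rules

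*Protocol*

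**What the plan says.** Section 4.1.2 lists as a secondary efficacy endpoint "Mortality or the need for RRT by 30 days post completion of surgery". Section 6.1.5 requires every randomized and transfused subject to have vital status and need for RRT "documented at Day 30 after surgery". It allows three sources: the medical record, a phone call to the subject or family, or an assessment "during the visit 28 ± 3 days after the last study transfusion". The third source carries a condition: "only if the last study transfusion was given at day 2 or later in the acute transfusion support period". The synopsis repeats this rule.

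Section 2.5 describes the same assessment with a different condition: the visit may be used "if the window covers 30 days after surgery time point".

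The footnote to Table 7.1e says only "Assess at Day 30 post surgery via clinic visit, medical record or phone call", with no window. Section 4.4 has study RBCs "transfused as needed starting from surgery at Day 0 until study post-operative Day 7" (or discharge or death, if earlier), so the last study transfusion can fall on any day from 0 to 7. Section 6.1.6 adds a "second follow up visit on Day 75 ± 15 days after the last study transfusion for vital status, need for RRT".

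**The concern.** The endpoint's clock starts at surgery, while the substitute visit's clock starts at the last study transfusion. The Day 2 condition is meant to bridge the two, but it appears to use the nominal visit day and to leave out the three days by which the visit may be early. A subject can satisfy the condition as written and still be seen before Day 30.

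At stake is the completeness of a named efficacy endpoint. A death or RRT start between an early visit and Day 30 would not be captured by the assessment that the protocol designates for it. In addition, a site that reads Section 2.5 and a site that reads Section 6.1.5 would apply different rules to the same patient.

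**Working it through.** **Inputs.** L is the day of the last study transfusion, 0 to 7 (Section 4.4). The visit is due 28±3 days after it (Section 6.1.5). The endpoint closes at Day 30 after surgery (Section 4.1.2).

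**Formulas.** Earliest visit = L + 25; nominal visit = L + 28; latest visit = L + 31.

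**Reproducing the stated cut-off.** L + 28 ≥ 30 gives L ≥ 2, so the protocol's Day 2 follows from the nominal day.

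**Allowing for the window.** L + 25 ≥ 30 gives L ≥ 5. Only a last transfusion on Day 5 or later guarantees that every permitted visit falls on or after Day 30.

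| L | Permitted visit days | Accepted by 6.1.5 and synopsis | Accepted by 2.5 (window contains Day 30) | Days short of Day 30 at the earliest visit |
|---|---|---|---|---|
| 0 | 25–31 | no | yes | 5 |
| 1 | 26–32 | no | yes | 4 |
| 2 | 27–33 | yes | yes | 3 |
| 3 | 28–34 | yes | yes | 2 |
| 4 | 29–35 | yes | yes | 1 |
| 5 | 30–36 | yes | yes | 0 |
| 6 | 31–37 | yes | no | 0 |
| 7 | 32–38 | yes | no | 0 |

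**Reading the table.** Under Section 6.1.5 the gap is at most three days, for L = 2, 3 or 4. The two conditions agree for L = 2 to 5 and disagree for L = 0, 1, 6 and 7, which is four of the eight possible days. Neither condition refers to the day on which the visit is actually held.

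**Size.** The documents give no 30-day rate for this composite. Assume 2% to 10%, with events spread evenly over 30 days. Assume also that every one of the 146 patients planned per arm had the last transfusion on Day 2 and was seen on the earliest permitted day. The expected number of events in the three-day gap is 146 × rate × 3/30:

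- at 2%: 146 × 0.02 × 0.1 = 0.29
- at 10%: 146 × 0.10 × 0.1 = 1.46

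The timing assumptions are deliberately extreme: last transfusions will be spread over several days and most visits will not be on the earliest one. The figures also precede any recovery of events from later data.

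**The case against.** The best defence is that the Day 2 clause only restricts use of the visit. Section 6.1.5 still demands status at Day 30, and Section 7.4 and Table 7.1e keep Day 30 as the target. On that view a Day 27 visit was never meant to satisfy the requirement. This does not fit the rule as written. The rule accepts last transfusions on Days 6 and 7, whose visit windows (31–37 and 32–38) never contain Day 30, and rejects Days 0 and 1, whose windows do. It turns on the transfusion day, not the visit day, and nothing in it excludes a Day 27 visit.

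The second defence is that other data fill the gap, and much of this stands. Death is an SAE (Section 7.3.1.2). SAEs are documented for 28 days after the last study transfusion (Section 6.1.4), which reaches Day 30 or later whenever L ≥ 2; the cut-off may even have been chosen for that reason, though no rationale is given. Vital status and need for RRT are asked again at Day 75±15. Most events, if dated, could therefore be recovered. Two limits remain. The protocol does not name these data as sources for the Day 30 endpoint, and they do not help for a patient with no record or contact after the early visit. Section 6.1.3 also drops the weekly call in the week of the visit, so an early visit may be the last contact before Day 30.

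A reader might also go further and infer from Section 2.5 that a visit as early as Day 25 is acceptable, since the window for L = 0 (25–31) contains Day 30. That is a literal reading of a background section. The synopsis and the procedural Section 6.1.5 both exclude last transfusions on Days 0 and 1. Section 2.5 shows that the document is inconsistent; it does not establish that Day 25 visits would be used.

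**Conclusion.** The point holds in limited form. As written in Section 6.1.5 and the synopsis, the visit that may supply Day 30 status can fall up to three days early (Day 27, 28 or 29 for a last transfusion on Day 2, 3 or 4). Section 2.5 states a condition that conflicts with this for Days 0, 1, 6 and 7. The day counts are exact and need no assumption.

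The practical loss is small: roughly 0.3 to 1.5 events per 146 patients under the assumed 2% to 10% rate and the extreme timing above, before recovery from SAE records or the Day 75 contact. It would be wrong to infer a bias between arms. The trial is blinded, the same rule applies to both arms, and nothing in the document suggests that visit timing differs between them. The primary endpoint and the sample size are unaffected. The correction is worth making because the sections must be reconciled in any case and the endpoint is a named efficacy endpoint.

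**What to change.** In the synopsis, Section 2.5 and Section 6.1.5, replace both conditions with one rule: the 28±3-day visit may supply the Day 30 status only if it takes place on or after post-operative Day 30; otherwise use the medical record or a phone call, dated on or after Day 30.

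State also that the endpoint is classified by the recorded date of death or RRT start, counting events on Day 30 or earlier. This is needed because an accepted visit can fall as late as Day 38, and an event on Days 31 to 38 must not be counted as a Day 30 event. For patients already assessed before Day 30, use the event dates obtained at the Day 75 contact.

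The cost is an edit in three places and a few extra record checks or calls of a kind that the protocol already permits.

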6.1.6 End of Study (75 ± 15 Days After Last Study Transfusion)

The complete list of assessments to be performed at the 75 ± 15 day study visit are outlined in Table 7.1e.

Subjects should be scheduled for a second follow up visit on Day 75 ± 15 days after the last study transfusion for vital status, need for RRT, and for assessment of INTERCEPT RBC-specific antibodies at end of study, either in hospital, clinic visit or off-site. In certain situations, it is possible for a mobile medical professional, authorized by the Sponsor and requested by site personnel, to conduct a home health service visit at a subject's home to collect these assessments. If the assessment of INTERCEPT RBC-specific antibodies is positive, the positive S-303 specific DSTR should be entered on the Adverse Event eCRF.

6.1.7 Assessments in Follow-up to a Reactive Antibody Test Specific for INTERCEPT RBCs

In the event of detection of treatment-emergent antibodies with specificity to INTERCEPT RBCs, the Investigator shall be instructed about specific laboratory and clinical assessments to be performed. See section 7.3.1.11 Suspected Hemolytic and Serologic TRs after Enrollment and Transfusion with Study RBC Components assessment of immune reactivity of INTERCEPT for more details.

6.2 CONCOMITANT AND EXCLUDED THERAPY

Standard medical care according to local institutional standards will be provided to each subject. The following concomitant (or planned) therapies/procedures will exclude subjects from the current study:

Cerus Corporation

Title: A Randomized, Double-Blinded, Controlled, Parallel Group, Non-inferiority, Phase III Study to Evaluate the Efficacy and Safety of the INTERCEPT Blood System for Red Blood Cells in Patients undergoing Complex Cardiac Surgery Procedures (the ReCePI study)

- Left-ventricular assist device (LVAD) or Extracorporeal membrane oxygenation (ECMO) support pre-operatively or planned need post-operatively.
- Cardiogenic shock requiring pre-operative placement of an IABP (Note: IABP done for unstable angina or prophylactically for low ejection fraction is not excluded).
- Treatment with any medication that is known to adversely affect RBC viability, such as but not limited to, dapsone, levodopa, methyldopa, nitrofurantoin, and its derivatives, phenazopyridine and quinidine.
- Planned use of autologous or directed donations
- Patients who have received an RBC transfusion during current hospitalization prior to randomization (within 7 days)
- Subjects who have received investigational products, including investigational blood products, pharmacologic agents or imaging materials, within the prior 28 days will also be excluded.

6.3 TREATMENT COMPLIANCE

Treatment compliance will be overseen by the Investigator and study staff and relevant documentation will be recorded in the eCRF. Compliance will be monitored by the Sponsor and/or Sponsor's representatives by review of source documents. The study RBC components will be labeled and tracked through all stages of processing of Test and Control components, storage, issue, and transfusion.

Cerus Corporation

Title: A Randomized, Double-Blinded, Controlled, Parallel Group, Non-inferiority, Phase III Study to Evaluate the Efficacy and Safety of the INTERCEPT Blood System for Red Blood Cells in Patients undergoing Complex Cardiac Surgery Procedures (the ReCePI study)

7 STUDY ASSESSMENTS

7.1 STUDY SCHEDULE OF ASSESSMENTS

A screen for antibodies specific for INTERCEPT RBCs should be performed every time that a routine IAT is performed during the acute 7-day study transfusion period.

A blood sample for sCr will be taken at 48 (± 4 hours) after completion of surgery, and sCr will be determined on a daily basis during the acute transfusion support period up to 7 days post-surgery. Other parameters will be collected on eCRFs only when available in the medical record.

For non-transfused subjects, a blood sample for sCr will be drawn at 48 ± 4 hours and daily sCr assessments will be recorded up to and including 48 ± 4 hours post surgery. All samples obtained for determination of human leukocyte antigen (HLA) will be stored for up to 1 year after the study has completed.

The study assessments used to evaluate both efficacy and safety are presented in **Table 7.1a, Table 7.1b, Table 7.1c, Table 7.1d, Table 7.1e and 7.2.**

Table 7.1a – Screening/Randomization

Study Period – Screening Visit (Day -30 to Day 0 pre-surgery)		
Assessment		Superscripts Defined
Informed Consent/Assent	X	
Demographics	X	
Indication /Type of scheduled surgery	X	
Medical, surgical, transfusion and medication history including radiographic contrast media within 7 days of surgery/ the need for irradiated RBC products	X	
¹. For Screening/Randomization purposes, data from medical records within 30 days prior to their surgical procedure may be used.
 
². See Table 7.2: Hematology and Chemistry Testing for details on required labs.

Number of prior pregnancies (females)	X	
Physical examination including height and weight	X	
Vital signs (HR, BP, RR) ¹	X	
Concomitant medications	X	
EKG ¹	X	
Pregnancy test (if applicable) ^{1,2}	X	
Hematology panel ^{1,2}	X	
Blood chemistry ^{1,2}	X	
Blood type ¹	X	
DAT ¹ , IAT ¹	X	
INTERCEPT RBC antibody screen (S-303-specific antibody screen)	X	
Sample for HLA antibodies	X	
TRUST score components	X	
Randomization [#]	X	[#] Eligible patients will be randomized up to 7 days before or on the day of surgery, but prior to the start of surgery (i.e., induction of anesthesia).
AEs/SAEs/TRs*	X	*The adverse event, serious adverse event and transfusion reaction collection period will begin at the start of surgery or the first study RBC transfusion, whichever is first. Adverse events (AEs) will not be collected for non-transfused subjects, but vital status will be recorded at the time of discontinuation.

Cerus Corporation

Title: A Randomized, Double-Blinded, Controlled, Parallel Group, Non-inferiority, Phase III Study to Evaluate the Efficacy and Safety of the INTERCEPT Blood System for Red Blood Cells in Patients undergoing Complex Cardiac Surgery Procedures (the ReCePI study)

Table 7.1b - Baseline (Pre-Surgery)		
Study Period – Baseline (Day -1 or Day 0 Pre-Surgery)		
Assessment		
Vital signs (HR, BP, RR) ³	X	² See Table 7.2: Hematology and Chemistry Testing for details on required labs.
Concomitant medications ³	X	
Pregnancy test (if applicable) ^{2,3}	X	³ These assessments can be combined with screening assessments if screening visit is also on Day -1 or Day 0 Pre-Surgery.
Hematology panel ^{2,3}	X	⁴ Data collected on eCRFs only as available from medical records if performed as Standard of Care.
Blood chemistry ^{2,3}	X	
EKG ³	X ⁴	⁵ Hemodynamic Parameters: Peripheral O ₂ Saturation, Mean Arterial Pressure, Central Venous Pressure.
Hemodynamic Parameters ⁵	X ⁴	
Fibrinogen Troponin	X ⁴	
AEs/ SAEs/TRs*	X	*The adverse event, serious adverse event and transfusion reaction collection period will begin at the start of surgery or the first study RBC transfusion, whichever is first. Adverse events (AEs) will not be collected for non-transfused subjects but vital status will be recorded at the time of discontinuation.

Table 7.1c – Acute Transfusion Support Period

Study Period - Acute Transfusion Support Period (Surgery [Day 0] to Post-operative Day 7, hospital discharge or death, whichever is first)

Assessment	Day 0 Surgery	Day 1 - 7	Superscripts Defined
Vital signs (HR, BP, RR)	X	X ⁶	
Concomitant medications	X ⁷	X ⁶	
EKG	X ⁴	X ⁴	
Hematology panel ²	X	X ⁶	
Blood chemistry ²	X	X ⁶	
Serum Creatinine at 48±4 hours after end of surgery		X ¹⁰	
Hemodynamic Parameters ³	X ⁵	X ⁶	
Fibrinogen, Troponin	X ⁴	X ⁴	
Urine output ⁸	X	X ⁶	
Procedure details	X		
Study RBC crossmatch and Study RBC transfusion(s)/data	X	X	
DAT, IAT, INTERCEPT RBC antibody screen (S-303-specific antibody screen) ⁹	X ⁴	X ⁴	
All other blood components (including non- study RBCs) transfused, if any	X	X	
Estimated blood loss from surgery	X		
Estimated blood loss from other source including chest tube(s)		X ⁶	
AEs/ SAEs/TRs*	X	X ⁶	

Table 7.1c – Acute Transfusion Support Period**Study Period - Acute Transfusion Support Period (Surgery [Day 0] to Post-operative Day 7, hospital discharge or death, whichever is first)**

Assessment	Day 0 Surgery	Day 1 - 7	Superscripts Defined
			
assessments will be recorded up to and including 48 ±4 hours post surgery.
 
* The adverse event, serious adverse event and transfusion reaction collection period will begin at the start of surgery or the first study RBC transfusion, whichever is first. AEs including protocol specified AEs, TRs and SAEs (see Section 7.3) are collected through 28 days after the last study transfusion; also collected daily during acute transfusion support period. For non-transfused subjects, adverse events (AEs) will not be collected for non-transfused subjects, but vital status will be recorded at the time of discontinuation.

Table 7.1d – Post-Operative Period		
Study Period- Post-operative Period Day 8 (or Post-discharge, if Earlier) to Day 28 after last study transfusion		
Assessment	Day 8 through to Day 28 post last study Tx	Superscript Defined
Weekly telephone calls	X	
Concomitant medications	X ⁴	
Hematology panel ^{2, 10}	X ⁴	
Blood chemistry ^{2, 10}	X ⁴	
Hemodynamic Parameters ⁵	X ⁴	
Fibrinogen, Troponin	X ⁴	
Urine output ⁸	X ⁴	
All other blood components (including non- study RBCs) transfused, if any	X ⁴	
AEs/ SAEs/TRs*	X	
². See Table 7.2: Hematology and Chemistry Testing for details on required labs
 
⁴. Data collected on eCRFs as available from medical records if performed as Standard of Care.
 
⁵. Hemodynamic Parameters, if available- Peripheral O₂ Saturation, Mean Arterial Pressure, Central Venous Pressure
 
⁸. Urine output data collected daily while a urinary catheter is in place. The date entered should reflect the start of the collection and match the visit date.
 
¹⁰. Laboratory results recorded in the eCRFs during this period will only be those assessed as clinically significant by the Investigator.
 
* The adverse event, serious adverse event and transfusion reaction collection period will begin at the start of surgery or the first study RBC transfusion, whichever is first. AEs including protocol specified AEs, TRs and SAEs (see Section 7.3) are collected through 28 days after the last study transfusion; also collected daily during acute transfusion support period. Adverse events (AEs) will not be collected for non-transfused subjects, but vital status will be recorded at the time of discontinuation.

Table 7.1e - Follow-up Visits (Day 28±3, 30, and 75±15)					
Study Period (Day 28±3, 30, and 75±15[End of Study])					
Assessment	28±3 days After last study transfusion or Early Termination	30 days After Surgery	End of Study (75±15 Days After Last Study Transfusion)	Superscripts Defined	
Vital signs (HR, BP, RR)	X			
2. See Table 7.2: Hematology and Chemistry Testing for details on required labs
 
* The adverse event, serious adverse event and transfusion reaction collection period will begin at the start of surgery or the first study RBC transfusion, whichever is first. AEs including protocol specified AEs, TRs and SAEs (see Section 7.3) are collected through 28 days after the last study transfusion; also collected daily during acute transfusion support period. Adverse events (AEs) will not be collected for non-transfused subjects, but vital status will be recorded at the time of discontinuation.
	
Concomitant medications	X				
Hematology panel ²	X				
Blood chemistry ²	X		X		
DAT, IAT	X				
INTERCEPT RBC antibody screen (S-303-specific antibody screen)	X				
Sample for HLA antibodies	X				
All other blood components (including non- study RBCs) transfused, if any	X				
AEs/ SAEs/TRs *	X				
Documentation of vital status and need for RRT	X	X ¹¹	X	
¹¹. Assess at Day 30 post surgery via clinic visit, medical record or phone call. Any RRT that is provided prophylactically during surgery while the subject is on a bypass machine does not meet this endpoint.
	

Table 7.2: Hematology and Chemistry Testing- Required (R) results and Where Available (WA)^a results

Study Period	Screening / Randomization		Acute Transfusion Support Period (Surgery [Day 0] to Post-operative Day 7, hospital discharge or death, whichever is first)		Post-operative Period	Follow-up Visit
		Baseline (Pre-surgery)				
Window	Day -30 to Day -1	Day -1 or Day 0 pre- surgery ^g	Day 0 Surgery	Days 1 – 7, hospital discharge or death	Days 8 to 28 after last study transfusion / death Laboratory results recorded in the eCRFs during this period will only be those assessed as clinically significant per the investigator.	28±3 days after last study transfusion or Premature Discontinuation Visit
Pregnancy test (if applicable)	R ^j	R ^j				
Hematology (CBC):						
Hematocrit (Hct)	R ^b	WA	R	R ^{d,e,i}	WA	R
Hemoglobin (Hb)	R ^b	WA	R	R ^{d,e,i}	WA	R
Platelets (PLT)	R ^b	WA	R	R ^{d,e,i}	WA	R
RBC Count	R ^b	WA	R	R ^{d,e,i}	WA	R
WBC Count	R ^b	WA	R	R ^{d,e,i}	WA	R
Fibrinogen		WA	WA	WA ^d	WA	
Troponin		WA	WA	WA ^d	WA	
Blood chemistry:						
Alkaline Phosphatase (ALP)	WA	WA	WA	WA ^d	WA	WA
Alanine Transaminase (ALT)	WA	WA	WA	WA ^d	WA	WA
Aspartate Aminotransferase (AST)	WA	WA	WA	WA ^d	WA	WA
Bicarbonate (CO ₂)	WA	WA	WA	WA ^d	WA	WA
Blood Urea Nitrogen (BUN)	R ^b	R	R ^h	R ^{d,h,i}	WA	R
Calcium (Ca)	R ^b	WA	R	WA ^d	WA	R
Chloride (Cl)	R ^b	WA	R	WA ^d	WA	R
Creatinine (sCr)	R ^b	R	R ^h	R ^{c,e,f,h,i}	WA	R
Glucose	R ^b	WA	R	R ^{d,i}	WA	R
Lactate Dehydrogenase (LDH)	WA	WA	WA	WA ^d	WA	WA
Potassium (K)	R ^b	WA	R	R ^{d,i}	WA	R
Sodium (Na)	R ^b	WA	R	R ^{d,i}	WA	R

Cerus Corporation

Title: A Randomized, Double-Blinded, Controlled, Parallel Group, Non-inferiority, Phase III Study to Evaluate the Efficacy and Safety of the INTERCEPT Blood System for Red Blood Cells in Patients undergoing Complex Cardiac Surgery Procedures (the ReCePI study)

Study Period	Screening / Randomization		Acute Transfusion Support Period (Surgery [Day 0] to Post-operative Day 7, hospital discharge or death, whichever is first)		Post-operative Period	Follow-up Visit
		Baseline (Pre-surgery)				
Window	Day -30 to Day -1	Day -1 or Day 0 pre- surgery ^g	Day 0 Surgery	Days 1 – 7, hospital discharge or death	Days 8 to 28 after last study transfusion / death Laboratory results recorded in the eCRFs during this period will only be those assessed as clinically significant per the investigator.	28±3 days after last study transfusion or Premature Discontinuation Visit
Total Bilirubin	R ^b	R	R	R ^{d,i}	WA	R

Footnotes:

^a R= required testing and reporting.

WA=where available. Data collected on eCRFs as available from medical records if performed as Standard of Care.

^b For Screening/Randomization purposes, data from medical records within 30 days of surgery may be used as long as laboratory tests are performed again prior to surgery in order to establish baseline values and confirm the subject's continued trial eligibility.

^c A sample to measure sCr will be taken at 48±4 hours after the end of surgery and captured on a specific CRF page for that time-point. For non-transfused subjects, a blood sample for sCr will be drawn at 48 ± 4 hours.

^d If an assessment is performed more than once in a day, the first set of results should be entered into the eCRF.

^e If a subject is discharged prior to the end of the acute transfusion support period (Day 7) but for any reason returns to the study site (e.g., re-hospitalization or standard care) within this acute transfusion support period, lab values routinely collected as standard of care should be recorded in the eCRF.

^f If serum creatinine is measured multiple times in a day, the worst daily value should be recorded in the eCRF.

^g These assessments can be combined with screening assessments if screening visit is also on Day -1 or Day 0 Pre-Surgery.

^h Assessments that contribute to the AKI should be measured at approximately the same time every day during the treatment period.

ⁱ These assessments are required to be collected daily on Day 1 through Day 7 post surgery or until discharge. If subject returns after discharge for a postoperative standard of care visit, assessments will be collected in eCRFs on the appropriate study day.

^j Negative urine or serum pregnancy test.

Cerus Corporation

Title: A Randomized, Double-Blinded, Controlled, Parallel Group, Non-inferiority, Phase III Study to Evaluate the Efficacy and Safety of the INTERCEPT Blood System for Red Blood Cells in Patients undergoing Complex Cardiac Surgery Procedures (the ReCePI study)

